23.0 Process to Document Consent in Writing

Research staff at the site will document the consent/assent response of each the parent and child during this process and the date and time it was obtained in the secure study database. Please see attached “Fact Sheet” for minors and adult participants which will be emailed/mailed and read aloud to the participants over the phone.

24.0 Setting

24.1 Describe the sites or locations where your research team will conduct the research.

The setting where all research procedures will take place except screening and informed consent and the intervention will be at the University of Pittsburgh ETUDES phone center.

Potential participants will be identified in the site’s clinical settings via telehealth appointments (or in person if the COVID-19 pandemic permits). Trained clinicians will have access to a specific view in the CCDC/ETUDES database referenced in data management procedures to enter participant information to confirm eligibility and document date/time/response of participants during informed consent discussion.

25.0 Resources Available

25.1 Describe the resources available to conduct the research:

During already scheduled appointments, clinicians trained at the site will approach and “pitch” the study to between 10-20 patients to pilot the BRITE app and suite of tools. This will be done over the phone via telehealth appointments during the COVID-19 pandemic. Site clinicians will be engaged in regular team meetings to review work and problem solve on the ground at their site.

26.0 Multi-Site Research*

26.1 Study-Wide Number of Subjects: 50

26.2 Study-Wide Recruitment Methods*

All recruitment methods will be under the control of the local site. Specific clinicians who are trained at each site will ask patients on their own caseload at the time of scheduled appointments if they want to participate in using the app and the associated research phone calls. Site clinicians may use BRITEPath advertising material to provide additional information to patients before they agree to answer screening questions and complete the informed consent over the phone. No community sampling or other methods will be used to advertise for participants at the site.

26.3 All participating sites will be engaged on bi-weekly team meeting conference calls to review procedures, problems, and enrollment targets.

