We recognize the limitations of the proposed stepped wedge study design for evaluating the effectiveness of BRITEPath, once a practice enters their intervention phase, assignment to BRITEPath cannot be concealed. This concern is somewhat mitigated by blind follow-up assessors. Alternative study designs (e.g., randomized control trial) pose significant implementation challenges. Clinicians may be hesitant to deliver TAU once the BRITEPath intervention is known, which could lead to study condition contamination (e.g., BRITEPath strategies introduced into TAU condition) and nonrandom patient assignment to condition (e.g., more high acuity patients referred to BRITEPath). In a stepped wedge design these feasibility concerns are addressed by the eventual assignment of all participating practices to the intervention condition and BRITEPath can be offered to all patients moving forward. Additionally, these designs are consistent with our broader goal of enhancing participant and community stakeholder engagement with the ETUDES Center. Results from this pilot trial will allow us to estimate the effect size of the BRITEPath intervention compared to TAU for reducing suicide risk in pediatric primary care. If our initial results show promise, these effect size estimates would be used to design a larger and adequately powered randomized control trial of BRITEPath.

SCREENING

Trained research staff or site staff will determine appropriate potential participants to refer and either refer via email, phone, or in person when staff person is on site. Site staff will review medical record or be made aware of the potential participant's chief complaint at presentation to the clinical setting to determine eligibility. At the time of identifying an eligible participant, trained research staff will complete verbal eligibility screen (with parent if a minor participant is involved or with adult participant). Upon eligibility, trained research site staff will enter participant contact information and date of birth into University of Pittsburgh secure webapp saved behind a firewall. This will create an "ID" which

PROTOCOL TITLE: The Center for Enhancing Treatment & Utilization for Depression and Emergent Suicidality Phase 1b-Study 3-BRITEPath

will communicate with the electronic Guide2Brite to create a profile for the participant in the secure BRITEPath web app.

STUDY INTERVENTION

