Only medical information that is necessary to conduct the study intervention will be collected. This will include diagnostic records, referral information, dates, times, outcomes of patient appointments, notes pertaining to patient appointments, who in the EMR prescribed/referred patients to use the intervention, PHQ-9 responses & scores, Service utilization (# visits-PCP, Mental Health specialty, ER, hospitalizations); pharmacotherapy; medical/psychiatric comorbidity; insurance coverage, matching referrals provided by PCP to expert opinion, Use of technical components of interventions & webportals, # of providers engaging in training/intervention, % representation at practice site, # practices who deliver intervention, and any other information needed for cost analysis purposes.

As with the informed consent & assent, it is not practical for researchers to conduct any ETUDES research activities, including the HIPAA authorization for BRITEPath on site due to the time and work flow constraints that emerged from formative qualitative data collection prior to this trial. The providers identified the time constraint of about 5 minutes of patient interaction that would be allowed for

PROTOCOL TITLE: The Center for Enhancing Treatment & Utilization for Depression and Emergent Suicidality Phase 1b-Study 3-BRITEPath

researchers to implement eligibility screening only. Thus the BRITEPath intervention, including informed consent and obtaining any necessary HIPAA authorization, was developed based on pilot focus groups and Phase 1a focus groups & interviews to be implemented without impacting the clinical work flows.

Further, the vast majority of participants recruited across sites are not near the research offices in Pittsburgh. It would put undue burden on the research participants to complete in-person consent, baseline, & follow up assessment visits to ask them to come to instead of using verbal consent in their "real world" setting (especially due to telehealth activities since the COVID-19 pandemic).

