10.0 Inclusion and Exclusion Criteria*

Individuals will be screened for eligibility via phone or after presenting to the site's clinical setting with an eligibility script and inclusion/exclusion questions. Responses to the questions will be entered into a secure study database managed by the University of Pittsburgh housed on a secure, encrypted server behind University firewall. Individual logins will be provided to research/site staff associated with this project.

Inclusion Criteria:

- Youth aged 12-26 yo
- Own a device (e.g. smartphone, ipod, tablet) with capability to download BRITE app
- Biological or adoptive parent is willing to provide informed consent for teen to participate
- Youth speaks and understands English
- Positive PHQ score or provider determines patient has depressive symptoms based on clinical interaction and refers youth to the study (in cases when PHQ is not available OR provider/parent have concern that youth/patient has a mood or behavioral problem
- Family agrees to see a MH staff at the site

Exclusion Criteria:

- Non English speaking
- No parent willing to provide informed consent for minors
- No cell phone capability of downloading BRITE app
- Is currently experiencing mania or psychosis symptoms that would prevent participant from understanding/participating
- Evidence of an intellectual or developmental disorder (IDD)
- Life threatening medical condition that requires immediate treatment (included emergent suicidality, homicidality, abuse/neglect, or other mental or physical condition)
- Other cognitive or medical condition preventing youth from understanding study and/or participating.
- Adults unable to consent
- Pregnant women-not specifically included or excluded as intervention and research procedures conducted will not inquire if a woman is pregnant.

-Prisoners excluded

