12.0 Local Number of Subjects

We expect to recruit about 10 subjects locally at each site onboarded to BRITEPath study as eligible and completed informed consent, and intervention with site clinicians.

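### Nothing in the plan makes recruitment comparable between the TAU and BRITEPath periods, so the stepped wedge only partly addresses the non-random patient mix it is said to address

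*Combined protocol and SAP*

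**What the plan says.** **Why this design.** Section 6.0 argues against an individually randomised trial partly because it could lead to "nonrandom patient assignment to condition (e.g., more high acuity patients referred to BRITEPath". It continues: "In a stepped wedge design these feasibility concerns are addressed by the eventual assignment of all participating practices to the intervention condition". Only the order in which clinics cross over is randomised (Sections 6.0 and 17.0). Section 6.0 also concedes that the condition cannot be concealed once a clinic has crossed, and offers blinded follow-up assessors as partial mitigation.

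**Who is recruited, and by whom.** Section 26.2 states "All recruitment methods will be under the control of the local site", and trained clinicians there "will ask patients on their own caseload at the time of scheduled appointments". Section 25.0 says clinicians "will approach and “pitch” the study to between 10-20 patients to pilot the BRITE app and suite of tools". Section 12.0 says "We expect to recruit about 10 subjects locally at each site onboarded to BRITEPath study". Section 10.0 allows eligibility by either of two routes: "Positive PHQ score or provider determines patient has depressive symptoms based on clinical interaction and refers youth to the study". Section 13.0 has clinicians scanning intakes for eligibility, but does not say that each eligible patient is invited.

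**What the analysis does about it.** Section 17.0 plans t-tests and chi-square tests of baseline differences, and characteristics that differ then enter the effect models as covariates. Section 13.0 places the research baseline call after the intervention has been delivered. Section 6.0 lists "PHQ-9 responses & scores" among the medical record items to be collected.

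**The concern.** Randomising the crossover order balances clinics over calendar time in expectation. It does not balance patients who are identified and invited one at a time after the clinic's phase is known. If clinicians approach sicker patients, or patients keener on an app, once BRITEPath is available, the two conditions differ in patient mix, and the later crossover of the remaining clinics does not undo this.

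Two uses of the data depend on comparability. Hypothesis 1b (Section 2.0) compares BRITEPath with TAU on depressive symptoms, distress, suicidality and functioning. Section 6.0 intends the resulting effect sizes to inform a larger trial. Selection bias is not reflected in a confidence interval, so it would pass unseen into that planning. The feasibility criteria (75% use) do not depend on this comparison.

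**Working it through.** **1. The plan's own figure.** Section 17.0 gives a 95% CI width of no more than 0.28 for N = 50. The Wald width at p = 0.5 is 2 × 1.96 × √(0.5 × 0.5 / 50) = 0.277, so the figure reproduces. It concerns a feasibility proportion and says nothing about comparability of the conditions. The plan gives no effect size, SD, ICC or TAU:BRITEPath split.

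**2. What each safeguard reaches.**

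| Safeguard | Section | Steering within a clinic-period | Different patients in TAU and BRITEPath periods |
|---|---|---|---|
| One condition per clinic at a time | 6.0, 17.0 | Prevented | Not prevented |
| Blinded assessors | 6.0 | No bearing | No bearing; protects outcome measurement |
| Scanning intakes | 13.0 | No bearing | Would help only if all eligible patients were then invited in both phases, which is not stated |
| Reach comparison | 17.0 | No bearing | Compares recipients with opt-outs, so it would not show the shift |
| Covariates after baseline tests | 17.0 | No bearing | Partial; measured differences only |

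**3. Possible size of the bias.** All inputs here are assumptions from outside the documents: half of eligible patients are invited; the clinician's preference correlates ρ = 0.2 to 0.5 with severity, in one phase only; severity correlates r = 0.5 to 0.6 with outcome.

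- Mean of a standard normal variable in its upper half: √(2/π) = 0.798.
- Shift in mean severity = ρ × 0.798: 0.16 SD (ρ = 0.2), 0.24 SD (ρ = 0.3), 0.40 SD (ρ = 0.5).
- Bias before adjustment = shift × r: from 0.16 × 0.5 = 0.08 SD to 0.40 × 0.6 = 0.24 SD.

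**4. A second model as a cross-check.** Assume 40% high acuity under TAU; 50%, 60% or 70% under BRITEPath; and an outcome gap of 0.5 to 1.0 SD between acuity groups. Bias = (difference in share) × gap: 0.05-0.10, 0.10-0.20 and 0.15-0.30 SD. The order of magnitude is the same.

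**5. Would the baseline tests notice?** Assume 25 patients per condition and no clustering, so the SE of a mean difference is √(1/25 + 1/25) = 0.28 SD.

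- *t-test (normal approximation).* Power = Φ(shift/SE − 1.96) + Φ(−shift/SE − 1.96). This gives about 9% for a shift of 0.16 SD and 29% for 0.40 SD.
- *Chi-square test.* Power = Φ{[difference − 1.96 √(2p̄(1 − p̄)/25)] / √([p₁(1 − p₁) + p₂(1 − p₂)]/25)}. For 40% against 50%, 60% and 70% this gives about 10%, 29% and 57%.

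A covariate that enters only after a significant baseline difference would therefore usually be left out at most of these imbalances.

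**6. Timing.** The research baseline call comes after the BRITEPath session (Section 13.0; Section 22.0 gives the same order). Symptom scores from that call may already reflect treatment, so adjusting for them could remove part of the effect as well as part of the bias. A clinic PHQ-9 recorded before BRITEPath starts does not have this problem.

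**The case against.** **The design does what Section 6.0 needs.** The worry there is about concurrent arms, where a clinician could send acute patients to BRITEPath and others to TAU. One condition per clinic at a time closes that route. This stands, and it is why the claim should be narrowed and not deleted.

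**The plan already adjusts.** Section 17.0 carries differing characteristics into the effect models. This is a real safeguard, limited by steps 5 and 6 above.

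**The intent is to offer BRITEPath to everyone.** Section 6.0 calls offering it to only some patients impractical and foresees offering it to all. That expresses intent for the BRITEPath phase; it is not a recruitment rule for both phases.

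**The bias is speculative and small.** The inputs come from outside the documents. Selection common to both phases would largely cancel, so selection in one phase only is the unfavourable case. On a 25/25 split even 0.24 SD is below one SE (0.28 SD), in a pilot sized for feasibility. All of this is fair. It limits how serious the point is, but does not supply the missing rule.

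**Stronger readings to avoid.** A reader might infer that clinicians hand-pick the 10-20 patients, or that they already screen every intake. The text says neither; discretion is inferred from the absence of a rule. A reader might also infer that the BRITEPath sample will be sicker. Section 6.0 mentions that direction only as an example of what could happen in another design.

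**Conclusion.** The point holds as a risk left open by the plan, not as a demonstrated bias. The stepped wedge prevents steering within a clinic-period, but no provision makes TAU-period and BRITEPath-period enrolees comparable, and the planned adjustment may not make up for it. Neither the occurrence nor the direction of selection can be read from the documents. Under the assumptions in step 3 the unadjusted bias is 0.08-0.24 SD, which would carry into the effect sizes intended for the later trial. With about 50 patients, sampling error would probably be larger; unlike the bias, it is visible in the interval. The sponsor should make the change, but the feasibility aim does not depend on it.

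**What to change.** 1. **Sections 13.0 and 26.2:** state one rule for both phases. Eligible patients are invited in order of appointment until the period's target is met. The target has to be stated, since the plan gives only about 10 per site. Reconcile intakes (13.0) with existing caseloads (26.2) as the source of patients.
2. **Section 17.0:** prespecify adjustment of the effect models for the last clinic PHQ-9 recorded before BRITEPath starts (for TAU patients, before enrolment), whatever the baseline tests show. State how a missing PHQ-9 is handled.
3. **Section 18.0:** extend the CONSORT diagram already kept to show eligible, invited, declined and enrolled counts by phase. Record patient-level PHQ-9 for people who do not consent only if the IRB and HIPAA terms allow it.
4. **Section 6.0:** narrow the claim to say that the design prevents steering within a period but not differential recruitment between phases.

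**Cost.** Protocol wording, counts by phase and one covariate from a record already being collected. Clinicians lose discretion over whom to approach. PHQ-9 will be missing for some, since Section 10.0 admits patients without one. Two gaps would remain: provider judgement can still establish eligibility, and willingness to consent may still differ by phase.
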